## **Study Purpose**

The purpose of the study is to use ultrasound imaging to characterize tremor in subjects as they perform grasping motion. In addition, functional electrical stimulation will be applied to study best pathways to suppress tremor.

## **Eligibility**

- Participants without Tremors: be able bodied and between the ages of 18 and 90 years of age. Participants will fall under the able body category if they exhibit no movement disorders and can perform grasping motion with no inhibition. In addition, an ultrasound probe will be strapped to your hand/forearm
- Participants with Tremors: between the ages of 40 and 90 years old and who exhibit tremor in the forearm/hand during grasping motion, or who exhibit tremor once the grasp is completed, and the object is being held for several seconds.
  - Participants will fall under the tremor subject category if they either:
    - Exhibit tremor with re-emergent properties during the grasping motion and exhibit no other health conditions other than their symptoms of Parkinson's disease that impact tremor severity and impairs motion
    - Exhibit tremor during grasping motion and exhibit no other health conditions other than their symptoms of Essential Tremor that impact tremor severity and impairs motion
  - Participants who have an implanted Deep Brain Stimulator (DBS) may be recruited. In this case, tremor data will be recorded both while the DBS is on their standard settings, as well as while it is turned off. This task will be performed with the assistance of [name] and will simply use your patient programmer to turn the device on and off under his supervision.
    - When turning off your DBS system, we will plan to perform this 1-2 minutes prior to the start of each grasping trial. Cumulatively, throughout the course of the experiment (all trials of grasping), you may be asked to keep DBS switched off for approximately 18-30 minutes.

### **Inclusion Criteria (Parkinson's Tremor Group):**

1. At least 40 years of age, and no more than 90 years of age.
2. Meet UK Parkinson's disease brain bank diagnostic criteria
3. Have clinical evidence of tremor of one or both upper extremities defined as involuntary, rhythmic oscillations about any joint within the upper extremities.
4. Tremor amplitude must be at minimum 1 cm as determined by expert opinion by a movement disorders specialist. This will be determined by [name].
5. People with an implanted deep brain stimulation (DBS) system may participate
6. Due to the nature of measurements occurring during a grasp maneuver, the tremor must be deemed to become re-emergent with a fixed posture. This shall be defined by development of postural tremor that does not begin immediately upon grasping the vertical object, but instead with a delay in development of oscillatory movement of at least half a second as timed by a stopwatch, and

that may grow in amplitude over seconds to maximum amplitude without changing the force of the grasp at first. Note that within-individual intermittency and variability of tremor can be influenced by anxiety, stress, cold temperature, and fatigue. In an effort to reduce this variability, we will have you perform tasks in a comfortable area, providing up to 20 minutes to allow you to relax in a temperature-neutral location, and reduce anxiety

#### **Inclusion Criteria (Essential Tremor Group):**

1. At least 40 years of age, and no more than 90 years of age.
2. Meet diagnostic criteria for essential tremor as defined by the 2018 consensus statement on the classification of tremors by the International Parkinson and Movement Disorders Society task force on tremor.
3. Have clinical evidence of tremor of both upper extremities defined as involuntary, rhythmic oscillations about any joint within the upper extremities.
4. Tremor amplitude must be at minimum 1 cm as determined by expert opinion by a movement disorders specialist. This will be determined by [name].
5. People with an implanted deep brain stimulation (DBS) system may participate
6. Due to the nature of measurements occurring during a grasp maneuver, the tremor must be present during a fixed posture. This shall be defined by development of postural tremor beginning immediately upon grasping the vertical object. Note that within-individual intermittency and variability of tremor can be influenced by anxiety, stress, cold temperature, and fatigue. In an effort to reduce this variability, we will have you perform tasks in a comfortable area, providing up to 20 minutes to allow you to relax in a temperature-neutral location, and reduce anxiety

#### **Exclusion Criteria (Tremor Group):**

1. Muscle weakness as determined by Medical Research Council grade less than 5/5 on direct testing in the upper limb afflicted with tremor
2. Infection at the upper limb at time of assessment
3. Pre-existing, concomitant neuromuscular or cerebellar disorders
4. Use of medications that can alter the function of the neuromuscular junction.
5. Those with both essential tremor and Parkinson's disease as determined by history or confirmed by movement disorders specialist prior to assessments. This will be determined by [name].
6. You cannot participate in this study if you do not exhibit tremor during the grasping and holding motion.

In addition, an ultrasound probe will be strapped to your hand/forearm in order to measure the ultrasound activity as grasping is performed and if you have hair on your forearm you may be asked to shave before attaching the probe to your forearm. You cannot participate in the study if you are uncomfortable with this.

## **Protocol**

Participants will be asked to perform different grasping motions with an ultrasound probe strapped to their forearm.

The initial number of visits to participate in the study will be 3, with each visit lasting an average of 1-2 hours, not exceeding 3 hours. These visits may be less or more depending on the quality of the collected data. If additional data is needed, participants may be invited to take part in up to 4 additional sessions. In total, you may take part in 3-7 visits.

The following procedures are experimental:

The experiment will start by securing up to two ultrasound probes, muscle signal recording sensor, and an inertial sensor to your hand/forearm. The probes will be strapped in such a way that the participants can still move their hand and forearm to perform grasping and pinching activities while their muscles are being imaged. In order to make sure the probes are securely strapped and captures the proper muscles, participants will be seated and then asked to grasp a object that is placed in a vertical upright position right in front of them.

To enhance the experimental setup, a wearable ultrasound transducer will be added to the existing sensors. This innovative device has been designed to conform to the shape of your limb, ensuring that it remains in place while you perform various activities. This allows continuous collection of forearm muscle ultrasound data and real-time analysis of muscle states, without restricting forearm movement. The device will be securely fastened to their forearm using medical tape, remaining non-invasive and comfortable to wear throughout the experiment.

Once it is certain that the correct muscles are being imaged through the duration of the grasping motion, data will be collected. The experiment involves grasping the object three different times, each time exerting a different force. The force will be measured through force sensors placed on the object and will be displayed along with the desired force. Before each trial you will be asked to attempt to grasp the object with the desired force in order to make sure it is achievable. This task will be repeated to image different muscles of the forearm that might cause tremor.

### **Recording and images**

During the grasping motion, video recordings will be taken of each trial. The video recordings will only be of the forearm/hand region and will not include any identifiable facial features. Video recording is optional and you can request to not have it done at any point during the study.

### **Risks and benefits**

There are minimal risks associated with participation in this research. The risks because of this research include restricted forearm movement due to the ultrasound probe being strapped onto the hand, and possible skin irritation due to Velcro or ultrasound gel.

The risks/discomforts should be no different for participants with DBS. There would be a minor inconvenience when turning off your device, no different than if they did this voluntarily with the patient programmer at home, in that tremor would worsen while the stimulation is off. This instance would be similar if they chose to turn off their device to save battery life on their hardware.

The following are physical risks that may occur because of using FES in the study.

- A). Skin irritation and redness due to the application of functional electrical stimulation. There could be a tingling sensation near the electrode site. These risks are mild and generally go away once the electrodes are removed.
- B) Since it is an artificial means to produce muscle contractions, FES induces rapid muscle fatigue. The FES-induced muscle fatigue may cause pain. This risk can be avoided by reducing stimulation levels or stimulating within your comfort levels. To allow a person to recover from muscle fatigue, an appropriate amount of rest will be provided between successive experimental trials during a session.
- C) Potential hyperextension during the experimental procedure. The FES stimulation program will have automatic mechanical safety stops to avoid this situation.
- D) A rare risk of skin burn exist underneath the FES electrode. FES stimulators are FDA-approved and are designed to apply safe electrical current levels.

Additionally, here is a rare chance of skin reaction to ultrasound gel or adhesive tape.

### **Compensation**

For your participation in this study, participants will receive \$10/hour.

## STATISTICAL DESIGN

### A. Tremor Model Accuracy.

Hypothesis: The data-driven and ultrasound-based tremor prediction model improves wrist angle prediction during tremor compared to the use of accelerometers.

Statistical Plan. Primary endpoint is the patient-level mean NRMSE of wrist angle prediction during tremor, computed by averaging trial NRMSEs within subject. We will perform a within-subject comparison of the data-driven with ultrasound enhanced model versus the accelerometer-only baseline using the Wilcoxon signed-rank test (two-sided  $\alpha=0.05$ ), reporting the Hodges–Lehmann median paired difference and 95% bootstrap CIs; if  $>2$  models are included, we will first run a Friedman test with Holm–Bonferroni-adjusted post-hoc pairwise tests.

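### SAP section A: the bootstrap interval for the Hodges–Lehmann difference is not tied to the signed-rank test; with fewer than about 15–20 subjects it is too narrow and can contradict the p-value

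*SAP*

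**What the plan says.** In SAP section A (Tremor Model Accuracy), each subject contributes one normalised error per model, "computed by averaging trial NRMSEs within subject". The sample size for the test and the interval is therefore the number of subjects, not trials. The ultrasound-enhanced model is compared with the accelerometer-only model "using the Wilcoxon signed-rank test" at a two-sided 0.05 level. The effect is reported as the Hodges–Lehmann "median paired difference and 95% bootstrap CIs".

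The section does not name the bootstrap type (percentile, basic, BCa or studentized), the number of resamples or the resampling unit. It does not say how to read the result if interval and test disagree. The supplied text of both documents states no number of subjects.

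**The concern.** The Hodges–Lehmann estimate belongs to the signed-rank test. Inverting the exact test gives an interval for it that excludes zero exactly when the test rejects. A bootstrap interval has no such link. With few subjects the resampled estimates spread too little, so the interval is too short.

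Two things are at stake for the primary result of hypothesis A: error bars labelled 95% that cover less, and an interval that excludes zero beside a p-value above 0.05. In the second case a reader is likely to take the interval as support for the ultrasound model that the prespecified test did not give.

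**Working it through.** **Inputs.** From SAP section A: one paired difference per subject, two-sided signed-rank test at 0.05, nominal 95% bootstrap interval. Assumed, because the text does not state them: n from 6 to 30 subjects (n=5 shown as a limit), subjects resampled, and normal differences (heavy-tailed and skewed ones tried as well). Coverage does not depend on the standard deviation. Section A gives no sample-size or power figure to reproduce; the only figure to check is the nominal 95%.

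**Exact interval.** For differences d₁,…,dₙ, form the M = n(n+1)/2 Walsh averages (dᵢ+dⱼ)/2 with i ≤ j. Their median is the Hodges–Lehmann estimate. Let T be the signed-rank statistic and c the largest value with 2·P(T ≤ c) ≤ 0.05. The interval runs from the (c+1)th to the (M−c)th ordered Walsh average, with confidence 1 − 2·P(T ≤ c).

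- n=5: the smallest two-sided p is 2/2⁵ = 0.0625, so no 95% interval exists; the most available is 93.75%.
- n=6: c=0 and 2/2⁶ = 0.03125, so confidence is 96.9%. The interval runs from the smallest to the largest difference.
- n=10: c=8 and 2 × 25/1024 = 0.0488, so confidence is 95.1%.

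**Bootstrap interval.** Simulation with normal differences: 4,000 datasets per cell and 1,000 resamples for coverage; 3,000 datasets per cell for the width ratio and for the n=12 disagreement figure. Monte Carlo standard error is about 0.3 to 0.6 points. All columns are percentages except the last.

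| n | Percentile coverage | BCa coverage | Basic coverage | Exact interval, confidence | Percentile CI excludes 0 but exact test does not reject, no true effect | Median width, percentile ÷ exact |
|---|---|---|---|---|---|---|
| 6 | 86.2 | 86.2 | 82.4 | 96.9 | 10.4 | 0.55 |
| 8 | 91.0 | 91.0 | 88.3 | 96.1 | 5.0 | 0.80 |
| 10 | 92.2 | 92.6 | 88.7 | 95.1 | 2.6 | 0.88 |
| 12 | 93.2 | 93.2 | 90.0 | 95.8 | 3.3 | 0.87 |
| 15 | 92.8 | 93.1 | 90.2 | 95.2 | 2.2 | 0.92 |
| 20 | 93.5 | 93.7 | 92.2 | 95.2 | 1.4 | 0.94 |
| 30 | 94.4 | 94.3 | 93.1 | not run | 0.9 | not run |

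Repeat runs with other seeds agree within a few points. At n=6 percentile coverage ranged from 85% to 89%, and disagreement was about 10–12%.

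**Disagreement with a true effect of 0.5 SD.** The percentile interval excludes zero without rejection in 23% of datasets at n=6, 12% at n=8, 9% at n=10, 7% at n=15 and 5% at n=20. The reverse (test rejects, interval includes zero) occurred in 0.3% or fewer.

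**Example.** For the five differences 0.4, 0.9, 1.3, 2.0 and 2.6, the percentile interval is 0.65 to 2.30, yet the exact p is 0.0625.

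**Skewed differences.** The basic bootstrap drops to about 82% at n=10. The exact interval relies on symmetry and also slips. In separate runs of 20,000 datasets it covered the pseudo-median in 94.2% at n=20 (exponential), 94.4% at n=30 (exponential) and 94.3% at n=15 (lognormal). The percentile bootstrap covered 93.0% at n=20 (exponential), so the gain there is about 1 point.

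**The case against.** The strongest objection is that the size of the problem depends on a number of subjects that the supplied text does not give. The table runs from a shortfall of about 9 points at n=6 (95 − 86.2 = 8.8) to about half a point at n=30 (95 − 94.4 = 0.6). This stands: a reader might infer that the reported interval will certainly fall far short of 95%, and the documents do not support that.

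A reader might also infer that the primary test is invalid or its error rate inflated. It is not. Section A decides by the signed-rank test, and the interval is only reported beside it. Section B of the SAP differs, because equivalence there is concluded from the interval itself.

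It would also be too strong to say that the exact interval covers at least 95% at every n. It cannot at n=5, and for larger n the guarantee needs symmetric differences, which section A does not assert.

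The bootstrap type is open, and a studentized version was not tested, so the figures apply to percentile, BCa and basic intervals only. A bootstrap interval for this estimate is also a recognised large-sample choice. Naming the method and stating that the test governs would settle which result prevails, but it would not repair the coverage of a percentile, BCa or basic interval at small n.

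**Conclusion.** The point holds in conditional form, with minor severity. If the number of subjects is below about 15–20, a percentile or BCa interval is materially too narrow and can contradict the p-value, nearly always in favour of a difference. At 30 or more the effect is slight. The basic interval is worse at every n examined.

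This rests on assumed n, resampling of subjects, and normal differences for the main figures. The undercoverage also appeared with the heavy-tailed and skewed distributions tried. The decision on hypothesis A is unaffected so long as it rests on the signed-rank p-value alone.

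**What to change.** In SAP section A, replace the bootstrap interval with the exact 95% interval from inverting the signed-rank test (ordered Walsh averages), reported with the Hodges–Lehmann estimate. State that the p-value comes from the exact distribution too; interval and test then agree by construction. Note that the 95% guarantee applies to six or more subjects with symmetric paired differences, that coverage can fall to about 94% under skew, and that at n=5 no two-sided 95% interval exists.

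Standard software gives this interval with the test, so the change costs no extra data or analysis effort. The price is width: about 80% more at n=6 (1/0.55 = 1.82), 12–15% at n=10–12 (1/0.88 = 1.14; 1/0.87 = 1.15) and 4–6% at n=20 (1/0.94 = 1.06). Much of that is the amount by which the bootstrap interval was too short; at n=6 part of it reflects the exact interval's 96.9% confidence.

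If the bootstrap is kept, the SAP should name its type, resampling unit and number of resamples, and say that the test governs. That removes the ambiguity but not the undercoverage.

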### C. Tremor Suppression

Hypothesis. Afferent stimulation effectively suppresses tremor compared to baseline tremor with no stimulation

Statistical Plan. Primary endpoint is the within-subject tremor suppression ratio, defined as the percent reduction in RMS wrist tremor amplitude during stimulation compared to baseline. Differences across stimulation frequencies will be tested using a one-way repeated-measures ANOVA (within-subject factor: Frequency); if assumptions are not met, the Friedman test will be applied. Upon a significant omnibus result, pairwise frequency comparisons will be performed with Holm–Bonferroni correction, and we will report mean differences with 95% CIs.

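### SAP section A: with more than two models, the only hypothesised contrast most naturally waits for a Friedman test and shares alpha under Holm, which can cost power without better error control

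*SAP*

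**What the plan says.** SAP section A states a single hypothesis: "The data-driven and ultrasound-based tremor prediction model improves wrist angle prediction during tremor compared to the use of accelerometers". The endpoint is a subject-level mean NRMSE, so each subject contributes one value per model. The analysis is given as follows: "We will perform a within-subject comparison of the data-driven with ultrasound enhanced model versus the accelerometer-only baseline using the Wilcoxon signed-rank test", at two-sided 0.05.

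The same sentence then adds a rule for more than two models: "we will first run a Friedman test with Holm–Bonferroni-adjusted post-hoc pairwise tests". It does not say whether the Wilcoxon test at 0.05 is replaced or retained in that case. It lists no pairs, names no post-hoc test, and does not say what follows a non-significant Friedman test.

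SAP section C (Tremor Suppression) uses a similar sequence but writes the gate out: "Upon a significant omnibus result, pairwise frequency comparisons will be performed with Holm–Bonferroni correction".

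**The concern.** An omnibus test followed by adjusted pairwise tests suits a question about all models at once. Section A asks about one pair. If a third model is fitted, that pair is most naturally drawn into a procedure built for a question the hypothesis does not pose. It must then clear two extra hurdles, a Friedman test across all models and a Holm threshold shared with pairs of no primary interest. At stake is power for the primary contrast, since a real advantage of ultrasound could be missed only because another model was added. Fixing the order of testing would give the same family-wise protection without that loss.

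**Working it through.** **Inputs from the SAP.** One named contrast; Wilcoxon signed-rank; two-sided 0.05; Friedman and Holm if there are more than two models. The 0.05 is a design input. Section A has no derived figure to reproduce.

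**Inputs assumed, because the documents do not give them.** Three models; n = 10, 15, 20 or 30; independent normal errors with unit variance; mean error 0 for ultrasound and 1.2 for the accelerometer, so the paired standardised difference is 1.2/√2 = 0.85. The Friedman gate is at 0.05, post-hoc tests are exact signed-rank, and Holm covers all pairs.

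**Step 1: thresholds.** Three models give 3 × 2 / 2 = 3 pairs. Tested directly, the named contrast faces 0.05. Under Holm it faces 0.05/3 = 0.0167 if its p-value is the smallest, 0.05/2 = 0.025 if second, and 0.05 if third, provided the earlier steps reject.

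**Step 2: power for the named contrast (%).** The midway (mean 0.6) and far-worse (mean 3.6) cases use 40,000 simulated data sets per cell (standard error at most 0.25 points). The far-worse model is (3.6 − 1.2)/√2 = 1.7 SD worse than the accelerometer. The case of a third model equal to either named model uses 20,000 per cell (standard error at most 0.35 points).

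| | n=10 | n=15 | n=20 | n=30 |
|---|---|---|---|---|
| Direct test at 0.05 | 64.6 | 84.7 | 93.9 | 99.3 |
| Gate and Holm, third model midway | 33.7 | 58.6 | 76.4 | 93.9 |
| Points lost, midway | 30.9 | 26.1 | 17.5 | 5.4 |
| Points lost, third model equal to either (approx.) | 27 | 18–19 | 9–10 | 2 |
| Gate and Holm, third model far worse | 64.3 | 84.6 | 94.0 | 99.3 |
| Points lost, far worse | 0.3 | 0.1 | −0.1 | 0.0 |

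The far-worse differences are within simulation error of zero. Both hurdles contribute in the midway case. At n=10 the gate alone leaves 42.0% (22.6 points lost) and Holm alone leaves 40.3% (24.3 points lost). The two losses overlap and do not add.

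**Step 3: error rate under the natural reading.** With all three models equal (2,500 runs per setting, n = 10 to 20), the named contrast is rejected in about 0.044 to 0.050 of data sets if tested directly, and in 0.009 to 0.011 under gate and Holm. The rule is therefore valid and conservative for this contrast.

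**Step 4: error rate under a fixed order.** Test the named contrast at 0.05, and go on to Holm over the other pairs only if it rejects. If its null is true, any family-wise error requires that 0.05 test to reject. If its null is false, an error can arise only among the remaining pairs, which Holm controls at 0.05. Simulation at n = 10 to 30 agrees (standard error about 0.11 points). Family-wise error is 4.85 to 5.01% with all models equal, 4.77 to 5.03% with only the third model different, and 1.96 to 4.81% with the primary contrast real and one other pair null.

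**The case against.** The strongest reply is that this is contingent and partly a design preference. No third model is named, the two-model plan is sound, and omnibus followed by Holm is a legitimate choice when several models matter equally. This stands, and it keeps the point minor. It does not remove the point, because the SAP itself writes the contingency in while stating only one hypothesis.

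The power figures can also be challenged. Models predicting the same angle in the same trials may well have correlated errors. If the midway model's errors correlate 0.8 with those of the ultrasound model, the loss falls to 24 points at n=10 and 1 point at n=30. The SAP names no post-hoc test, and rank-sum tests would give other figures, including a loss in the far-worse case. The table shows that the cost can be material; it does not estimate this trial's loss.

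A reader might infer three stronger claims that the documents do not support:

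- *That section A is silent on how the contrast is handled.* The words *first* and *post-hoc* most naturally place it under Friedman and Holm, and the sequence in section C points the same way. An unadjusted Wilcoxon test standing alongside is possible, since that clause carries no condition, but it is the weaker reading.
- *That false positives are inflated.* Either rule, fixed in advance, controls error.
- *That a third model is expected because the Protocol describes "securing up to two ultrasound probes, muscle signal recording sensor, and an inertial sensor to your hand/forearm".* SAP section B already gives electromyography a use, as a reference for tremor frequency, so recording a muscle signal does not imply a muscle-signal model of wrist angle.

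**Conclusion.** The point holds as a minor, conditional loss of efficiency. If more than two models are analysed, the natural reading puts the only hypothesised contrast behind a Friedman test and inside a Holm family. The result is valid but can be less powerful than necessary. Under the assumptions listed, the cost is roughly 27 to 31 points at n=10 and 2 to 5 at n=30 for a third model equal to one of the two or midway between them, and none for a far worse one. It shrinks with sample size and with correlated errors. With only the two named models the cost is zero.

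**What to change.** State in SAP section A that one pre-named ultrasound-enhanced model is always compared first with the accelerometer-only baseline, by Wilcoxon signed-rank at two-sided 0.05, with no Friedman gate and outside the Holm family, however many models are fitted. Name any further models before analysis and list the other pairs as secondary. Test those with Holm-adjusted signed-rank tests only if the primary contrast is significant.

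This changes SAP wording only. There are two downsides: the other model comparisons are not formally tested if the primary contrast fails, and a second ultrasound candidate cannot carry the primary claim. If the sponsor does want all pairs treated equally, section A should say so and state the gate, the pairs and the post-hoc test. That would settle the wording but keep the power cost.
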